## 4 STUDY DESIGN

### 4.1 STUDY HYPOTHESIS

The central hypothesis of the study is that alterations of the microbiota in the maternal gut (dysbiosis) exacerbated by nutritional status or pathogen exposure during pregnancy, impacts weight gain during pregnancy because of impaired nutrient absorption, leading to corresponding negative birth outcomes.

**Figure 3: Project Hypothesis.** During the course of pregnancy a shift to an ‘unhealthy’ microbiome, perhaps triggered by exposure to pathogens, antibiotics or poor diet, results in impaired nutrient absorption, low weight gain and poor birth outcomes.

### 4.2 STUDY DESIGN

The study will be a prospective, longitudinal observational study to investigate the impact and relationship between prokaryotic and eukaryotic microbes in the gut and their association with maternal health and birth outcomes among young women, 17-24 years of age in Matiari District, Pakistan. The study will aim to recruit 400 women into two groups based on BMI at time of recruitment (Normal: BMI between 18.5 and 24.9 kg/m^2 and Low: BMI less than 18.5 kg/m^2, as defined by WHO guidelines[85]). Our goal is to recruit 200 participants with normal BMI and 200 participants with low BMI into the study. However, in the event that we have difficulty reaching this recruitment target, we will recruit more women into the normal weight BMI. The study will follow women and their infants over the course of their pregnancy and for a year post-partum, collecting stool and blood samples, nutritional information, health assessments, anthropometric measurements and empowerment metrics at different time points.

### 4.3 END OF STUDY DEFINITION

A participant is considered to have completed the study if she has completed all phases of the study including the last visit or the last scheduled procedure shown in *Section 1.3, Schedule of Activities (SoA)*. The duration of participation for each individual participant will vary depending on how long they are in the pregnancy monitoring cohort, upon conception the participants will

be followed for approximately 17-19 months in duration, from 10-14 weeks into their pregnancy, until one year post-partum.

It is estimated that it will take approximately 6 -8 months for the study to reach its recruitment target, and approximately 3 years from when the study opens to the final participant study visit.

## 5 STUDY POPULATION

This study will examine young, married women, including newlyweds, 17-24 years of age, living in Matiari District, Pakistan. We will focus on this younger demographic due to our lack of knowledge on the microbiome of young women, and their vulnerability to undernutrition[10]. This will be the first systematic investigation of the impact of the microbiome on nutritional status during pregnancy in young women and directly aligns with global health initiatives focused on this vulnerable cohort.

Upon identification of pregnancy, participants will be screened for eligibility and their pregnancy will be confirmed. If the woman is between 10-14 (+ 2 weeks) post-conception she will be invited to join the study. If she agrees to participate written informed consent will be obtained. Only one woman per household will be eligible to participate in the study.

### 5.1 INCLUSION CRITERIA

In order to be eligible to participate in the pregnancy surveillance cohort phase, an individual must meet all of the following criteria:

1. Consent provided
2. Married female aged 17-24 years
3. In good general health, with no comorbidities
4. Absence of COVID19 symptoms
5. Women who are 14 weeks post-conception or less (+ 2 weeks)
6. Intend to comply with study procedures and follow up

### 5.2 EXCLUSION CRITERIA

An individual who meets any of the following criteria will be excluded from participation in this study at the pregnancy surveillance cohort phase of the study:

1. Women who do not meet the enrollment age criteria
2. Women participating in interventional clinical trials
3. Women who intend to leave the study area
4. Women who cannot comply with study procedure's and follow-up
5. Illness and other co-morbidities
6. Signs of potential COVID19 infection
7. BMI higher than 24.9 kg/m^2
8. Women who already have a member of their household participating
9. Women who have taken antibiotics within the past 3 months
10. Women who are past 16 weeks post- conception

### 5.3 STUDY SETTING

This study will be conducted in the rural settings of Matiari District in Sindh province, Pakistan. Matiari is situated in North Eastern part of Sindh, about 200 km away from Karachi. Including 1,418 villages and a population of about 776,542, around 78,000 residents are young women 15-24 years (based on regular surveillance data). Approximately 20% of these women are married. The study setting has a well-established community and health system liaison, basic demographic surveillance, and field centers for research. This site has also been selected because it has been the location of several large cluster randomized trials, meaning that households are well mapped with household level GIS. This district is representative of typical conditions in Pakistan, and there is a close working relationship with community, civic society leaders, and public health department facilities. Select epidemiological features of the Matiari site are highlighted below in (Table 4) and findings to date from the household survey have been provided in (Table 5). These tables were taken from the MaPPS trial protocol. The current MaPPS baseline household listing data shows that the proportion of young women 15-19 and 20-24 years each comprise 5% of the population. The MaPPS trial was a prospective, cluster randomized evaluation of the effectiveness of supplementation with multiple micronutrients and life skills development education provided from preconception on health and birth outcomes among young, reproductive-age Pakistani women (15-24 years).

**Table 4. Epidemiological information from Matiari district (estimated from regular surveillance data)**

Characteristic	Matiari-specific observations
Population size	776,542
Villages	1,418
Households	112,542
Number of women 15-45 years of age	178,993
Number of women 15-24 years of age	77,740
Number of females 15-19 years of age	39,417
Mean ( $\pm$ SD) age at 1 st pregnancy (years)	20.3 $\pm$ 3.2
Mean ( $\pm$ SD) age at marriage (years)	17.7 $\pm$ 2.8
Number births in last year to women 15-45 years of age	27,178
Number of births to women 15-24 years of age	5979
Number of births to women 15-19 years of age	715
Birth rate (per 1000 population)	35

**Table 5. Key statistics to date from the MaPPS household survey (from data collected up to end of March 2017, including population size of 158,019)**

Characteristic	MaPPS catchment area-specific observations		
	15-24 years	15-19 years	19-24 years
Number of women	17,164	9,286	9,054
Number of pregnant women	983	226	813
Pregnancy rate (%)	6	2	9
Ratio of women to pregnancies	17.5	41.1	11.1

## 5.4 STRATEGIES FOR RECRUITMENT AND RETENTION

This study builds off the MaPPS trial partnership between Aga Khan University in Pakistan and [name] at SickKids. Led by Principal Investigator [name], this trial is an exciting partnership between SickKids' Centre for Global Child Health and the Institute for Global Health and Development, AKU. Here we will leverage the clinical network established by the MaPPS trial, to extend the trial to recruit hundreds of young mothers to investigate host-microbiome interactions in pregnancy.

The study will aim to recruit 400 married women into two groups based on BMI at time of recruitment (Normal: BMI between 18.5 and 24.9 kg/m^2 and Low: BMI less than 18.5 kg/m^2, as defined by WHO guidelines[85]). Our goal is to recruit 200 women with normal BMI and 200 women with low BMI. However, in the event that we are unable to reach this recruitment target, we will recruit more women in the normal BMI category. With an annual birth rate of 2% and Matiari Surveillance data revealing proportions of normal and low BMI individuals to be 49.7% and 29.8% respectively, we anticipate meeting our target sample size in the first year of the study.

### 5.4.1 METHOD FOR MONITORING NEW PREGNANCIES

From the MaPPS trial we found that women typically report their pregnancy to study personnel near the end of the first trimester or start of their second trimester. Field team shall implement multiple strategies to identify new pregnancies:

- 1) The MaPPS study was implemented in the LHW-covered area within the district, and LHWs are required to visit their catchment population once a month. LHWs are required to meet with their respective lady health supervisors (LHSs) in the first week of each month to report pregnancies and share data on several other indicators. Research field staff will join this meeting and get information about new pregnancies.
- 2) Research field staff will get contact numbers of women/families and make regular calls inquiring as to whether they think that they might be pregnant.
- 3) Research field staff will also identify volunteers from within local villages and primary health care facilities to notify them about new pregnancies. A communication card of Rs.100 will be provided to the volunteer against a valid pregnancy notification.
- 4) Research field staff will also employ random check of households and villages and meet with LHWs and volunteers in the field to get information on pregnancies.

Once potential pregnancies are identified by LHWs and volunteers, eligible individuals will be asked by them to provide verbal consent to have a research staff member contact them about the study. If the individual provides this verbal consent to contact, they will be contacted by study personnel at their home to confirm their eligibility. This will include the administration of a pregnancy test to confirm the pregnancy, questions to determine the gestational age (if the gestational age is 16+ weeks the individual will be excluded) and the collection of anthropometric measurements to confirm their BMI is equal to or below 24.9 kg/m^2. The aim will be to recruit participants during the 10-14 week period post-conception, however, women

can be enrolled in the study up to 16 weeks post-conception. Only one participant per household can be enrolled in the study.

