Objectives	
Primary Objective:
 
To assess if alterations of the microbiota in the maternal gut (dysbiosis) is associated with maternal gestational weight gain.
 
To determine the association between maternal microbiome dysbiosis during pregnancy and birth outcomes, infant growth, infant nutritional status and health in the first year of life.
 
Secondary Objectives:
 
To link the maternal microbiome to dietary intake, with a focus on calories and macronutrients.
 
To integrate maternal anthropometric factors, morbidity and mortality with microbiome data to reveal key modulators (microbial taxa and metabolites) of dietary intake during pregnancy and the post-partum period.
 
To determine the impact of the maternal microbiome during pregnancy, including the exposure to pathogens and parasites, on the development of the infant microbiome.
 
To investigate the maternal microbiome's exposure to pathogens and parasites, and the association with intestinal inflammation.
 
Exploratory Objectives:
 
To explore the role of the maternal gut microbiome during pregnancy and to identify gut community dynamics in pregnant women and how this impacts differences between dietary intake and nutritional status.
 
To investigate socio-economic factors; including gender, poverty, exclusion and empowerment, and their influence on the health of a mother's microbiome (assessed by alpha and/or beta diversity, and absence of pathogens).
 
To explore the role of the human microbiota on nutritional status by performing fecal microbiota transplants in germ free mice and sterile piglets.

Recruitment and Follow-up	

1) MV1: 10-14 weeks post conception

2) MV2: 30-34 weeks post conception

3) MV3/ IV1: 24-72 hours after birth

4) MV4/IV2: 3 months post-partum

5) MV5/ IV3: 6 months post-partum

	6) MV6/IV4:12 months post-partum  MV: Maternal Visit IV: Infant Visit
Study Population:	Pregnant, married women aged 17 to 24 years from the Matiari district, Pakistan and their infants.
No. of Subjects	400 women and their infants. • 200 subjects with normal BMI (18.5-24.9) at conception • 200 subjects with low BMI (less than 18.5) at conception
Study Duration:	The study duration will be approximately 3 years.

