### 3 STUDY OBJECTIVES

**Table 4: Study Objectives**

OBJECTIVES	ENDPOINTS	JUSTIFICATION FOR ENDPOINTS
Primary		
To assess if alterations of the microbiota in the maternal gut (dysbiosis) is associated with maternal gestational weight gain.	The primary endpoint will be maternal gestational weight gain (GWG) during pregnancy, measured between the first (10-14 weeks post-conception) and second time point (30-34 weeks post conception).  To monitor microbiome dynamics, 16S and 18S rDNA surveys will be	Weight gain is a key predictor of adverse birth outcomes[83, 84].

OBJECTIVES	ENDPOINTS	JUSTIFICATION FOR ENDPOINTS
	
applied to the maternal stool samples to monitor the bacterial and eukaryotic components of the microbiome.
	
To determine the association between maternal microbiome dysbiosis during pregnancy and birth outcomes, infant growth, nutritional status and health status in the first year of life.	
The specific birth outcomes evaluated will include preterm birth, birth weight, SGA, LGA, head circumference at birth, mortality, morbidity.
 
The specific infant outcomes evaluated will include the following growth and nutritional status parameters; WHO z-scores for weight, length, head circumference and MUAC during the first year.
 
Birth characteristics will be collected, including information on vaginal or cesarean birth (elective, emergency), placental insufficiency and antibiotic usage.
 
Infant morbidity and mortality will be assessed at follow-up visits, with questions regarding care-seeking, hospitalizations and treatments for any morbidity; including antibiotic usage.
 
For the infants an assessment of amount and mode of feeding will be obtained at 3-months, 6-months and 12-months.
 
To monitor microbiome dynamics, 16S and 18S rDNA surveys will be applied to the maternal stool samples to monitor the bacterial and eukaryotic components of the microbiome.
	
This will allow for an examination of the association between the maternal microbiome and birth outcomes.

Secondary		
To link the maternal microbiome to dietary intake, with a focus on calories and macronutrients.	
The maternal participants will complete a 24 hour dietary recall at both time points during pregnancy and at 1-year post-partum.
	
Quantitative measures of nutritional status will provide parameters to better inform microbiome analyses.

OBJECTIVES	ENDPOINTS	JUSTIFICATION FOR ENDPOINTS

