#### 9.4.1 ADDRESSING THE PRIMARY OBJECTIVES

This study has two primary objectives: 1) To assess if alterations of the microbiota in the maternal gut (dysbiosis) are associated with maternal gestational weight gain; and 2) To determine the association between maternal microbiome dysbiosis during pregnancy and birth outcomes, infant growth, nutritional status and health status in the first year of life.

The first objective will be addressed through the following approaches. First, maternal gut bacteria and eukaryotic profiles will be used to calculate Bray-Curtis dissimilarity metrics between individual samples which will be leveraged in principal co-ordinate analyses to determine the extent samples collected at the first or third trimester, exhibiting similar gestational weight gains, co-cluster. Permutational multivariate analysis of variance (PERMANOVA) tests will assess the degree of overlap between samples exhibiting low gestational weight gain versus samples exhibiting high gestational weight gain. A lack of clustering in the first trimester, followed by clustering of samples on the basis of similar gestational weight gain would indicate that alterations in the maternal microbiota during the course of pregnancy, impacts gestational weight gain. Next, we will attempt to correlate changes in the alpha diversity (as measured by the Shannon and Simpson indices) of the gut microbiome samples between the first and third trimester, with gestational weight gain. A decrease in alpha diversity (indicative of dysbiosis) associated with low gestational weight gain, would again indicate that dysbiosis is associated with maternal weight gain. To examine the influence of individual taxa on gestational weight gain, we will perform bivariate analyses that examine the correlation (Pearson, Spearman) of each taxon with gestational weight gain. Correlations will examine taxon abundance in first and third trimester, in addition to the change in abundance between the two trimesters. The Benjamini-Hochberg procedure will be applied to correct p-values while controlling for false-discovery rates.

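### Section 5.4.1 states the 16-week enrolment limit on two undefined time scales, so eligibility conflicts by up to two weeks

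*Protocol*

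**What the plan says.** Five places in the protocol bear on when a woman may enter the study.

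- Section 5 (Study Population): "If the woman is between 10-14 (+ 2 weeks) post-conception she will be invited to join the study".
- Section 5.1, inclusion criterion 5: "Women who are 14 weeks post-conception or less (+ 2 weeks".
- Section 5.2, exclusion criterion 10: "Women who are past 16 weeks post- conception".
- Section 5.4.1, on the questions asked at the screening contact: "if the gestational age is 16+ weeks the individual will be excluded".
- Section 5.4.1, next sentence: women "can be enrolled in the study up to 16 weeks post-conception".

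Four of the five count from conception. The screening instruction counts in gestational age. The protocol defines neither term and gives no conversion.

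Table 4 (Study Objectives) defines the primary endpoint, gestational weight gain, as "measured between the first (10-14 weeks post-conception) and second time point (30-34 weeks post conception". Section 9.4.1 then refers to the stool samples from these two visits as "samples collected at the first or third trimester".

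**The concern.** Gestational age is usually counted from the last menstrual period, about two weeks before conception. On that reading, two adjacent sentences of section 5.4.1 set upper limits two weeks apart, and the stricter one is the instruction used at the screening contact.

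The band in dispute is one where women can be expected. Section 5.4.1 itself reports that women usually disclose a pregnancy around the change from first to second trimester, and the protocol allows two weeks beyond the target window. Dating at screening rests on questions; the ultrasound form (M-3) is completed only for women who have the scan.

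The status of such a woman has consequences. Section 6 allows withdrawal when an exclusion criterion is recognised late, and section 10.5 treats any noncompliance with the protocol as a deviation. As written, the text does not settle whether a woman at 15 weeks post-conception is correctly enrolled.

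The undefined time origin also matters to the primary endpoint. Weight gain between two visits depends on the weeks between them, and that interval is already allowed to vary widely.

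**Working it through.** **Inputs from the protocol.** Upper limit at screening: gestational age 16+ weeks excluded (5.4.1). Upper limit elsewhere: 16 weeks post-conception (5.4.1 next sentence; 5.2; and 14 + 2 in 5 and 5.1). MV1: 10-14 weeks, with entry allowed to 16. MV2: 30-34 weeks. Participant duration: 17-19 months (1.1).

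**Assumed input.** Offset between the scales: 2 weeks if gestational age runs from the last menstrual period, 0 weeks if the authors use the terms as synonyms.

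**Step 1: does the stated duration show which scale was meant?** Months = (term − entry week) × 7 / 30.4375 + 12, with term assumed at 38 weeks post-conception or 40 weeks of gestational age.

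| Entry week | Post-conception scale (term 38) | Gestational-age scale (term 40) |
|---|---|---|
| 10 | 28 × 7/30.4375 + 12 = 18.4 | 30 × 7/30.4375 + 12 = 18.9 |
| 14 | 24 × 7/30.4375 + 12 = 17.5 | 26 × 7/30.4375 + 12 = 18.0 |
| 16 | 22 × 7/30.4375 + 12 = 17.1 | 24 × 7/30.4375 + 12 = 17.5 |

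All six values lie within 17-19 months. The plan's figure is reproduced on both scales, so it cannot settle the question.

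**Step 2: the limit with a 2-week offset.** Gestational age 16 is 16 − 2 = 14 weeks post-conception; 16 weeks post-conception is 16 + 2 = 18 weeks of gestational age. The screening rule stops at 14 weeks post-conception and the other four statements stop at 16. The disputed band, 14 to 16, is exactly the two-week allowance of sections 5 and 5.1. It is (16 − 14)/(16 − 10) = one third of the weeks in the 10-16 window. That is a share of weeks, not of women.

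**Step 3: the limit with a 0-week offset.** If 16+ means 16 or more, a woman at exactly 16 weeks is excluded by the screening rule. The next sentence enrols her, and exclusion criterion 10 does not remove her, because it applies only past 16 weeks. Only the boundary is in conflict.

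**Step 4: the trimester label.** Counted strictly from conception, entry at 10-16 weeks is 12-18 weeks of gestational age under the 2-week offset. On the usual division of pregnancy (again not stated in the protocol), much of that lies beyond the first trimester. Either the label or the strict meaning of post-conception does not hold.

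**Step 5: the interval behind the primary endpoint.** Shortest permitted: 30 − 16 = 14 weeks. Longest permitted: 34 − 10 = 24 weeks. A consistent offset cancels, since (MV2 + 2) − (MV1 + 2) = MV2 − MV1. The 14-24 week range is therefore the same on either scale.

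**Step 6: power.** The calculation in section 9.1 does not depend on dating. With r = 0.14 and N = 400, Φ(atanh(0.14) × √397 − 1.96) = 80.2%, which agrees with the stated 80%.

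**The case against.** The best defence is that this is one loose parenthesis in a recruitment narrative. The formal criteria agree with each other on 16 weeks post-conception, and eligibility is confirmed on screening form M-1, whose text is not shown. The protocol also seems to use the terms loosely: section 4.3 describes entry simply in weeks of pregnancy, and the first-trimester label in 9.4.1 points the same way. If so, the gap shrinks to the single boundary value. This stands to the extent that two weeks is an upper bound and not an established figure. It does not remove the conflict, because the terms remain undefined and the boundary differs on either reading.

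Several stronger inferences are tempting and are not supported.

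- *Every visit window shifts.* MV1 and MV2 are given in weeks post-conception throughout, and the screening parenthesis changes neither. The later visits are timed from delivery (the first of them "24-72 hours after birth") and cannot move.
- *The preterm definition shifts.* Table 4 lists preterm birth without a week threshold, so there is no stated definition to shift. Where timing at birth is recorded (form M-8, section 7.2.1.4, Table 8), the term used is gestational age. A rate of misclassified births would require an error that no section prescribes.
- *Measured weight gain is off by a fixed amount in kilograms.* That needs one woman's two visits to be dated on different scales, which nothing in the text calls for; a consistent offset cancels.

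Nor is the missing lower limit in inclusion criterion 5 clearly an error. Section 5.1 says that its criteria apply to the surveillance phase, and section 5 supplies the 10-week start.

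**Conclusion.** The concern holds in a narrow form. Section 5.4.1 gives the upper enrolment limit on two undefined scales. The conflict is 0 to 2 weeks: the full band from 14 to 16 weeks post-conception if gestational age runs from the last menstrual period, or only the status of exactly 16 weeks if the terms are synonyms and 16+ includes 16. The two-week figure rests on a convention that the protocol does not state. The number of women affected cannot be derived from the document.

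The first-trimester wording in section 9.4.1 is a second sign that the time origin is unsettled. Sample size and power are unaffected. For the primary endpoint, the point to act on is the permitted MV1-MV2 interval of 14 to 24 weeks, which makes exact dating at both visits worth recording and using.

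**What to change.** 1. Define one time origin and state how it relates to any other term that is kept.
2. State one upper enrolment limit on that scale, in completed weeks and days, saying whether 16 weeks and 0 days is in or out. Reconcile sections 5, 5.1, 5.2 and 5.4.1 to it. Which limit and which scale to use is for the investigators to decide.
3. Reword the trimester labels in section 9.4.1 so that they match the MV1 and MV2 windows on the chosen scale, or refer to the visits by name.
4. Record the exact week on that scale, and its source (ultrasound or recall), at MV1, MV2 and birth.
5. Use each woman's actual MV1-MV2 interval in the gestational weight gain analysis, for example as a covariate or by analysing gain per week. If an analysis plan already does this, a cross-reference is enough.

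The cost is protocol and form wording, plus one derived variable in the analysis. No new procedure or visit is needed.
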